#### Simulation Results for Arm D

| Scenario | Assumed true response rate | Pr(Stop for inferiority) | Average # patients treated (10%, 25%, 50%, 75%, 90%) |
|----------|----------------------------|--------------------------|--|
| 1        | 0.1                        | 0.876                    | 15.4 (10, 10, 15, 20, 20 )                           |
| 2        | 0.15                       | 0.662                    | 17.3 (10, 15, 20, 20, 20 )                           |
| 3        | 0.2                        | 0.434                    | 18.51 (10, 20, 20, 20, 20 )                          |
| 4        | 0.25                       | 0.243                    | 19.25 (20, 20, 20, 20, 20 )                          |
| 5        | 0.3                        | 0.119                    | 19.61 (20, 20, 20, 20, 20 )                          |
| 6        | 0.35                       | 0.047                    | 19.86 (20, 20, 20, 20, 20 )                          |
| 7        | 0.4                        | 0.021                    | 19.92 (20, 20, 20, 20, 20 )                          |
| 8        | 0.45                       | 0.008                    | 19.96 (20, 20, 20, 20, 20 )                          |
| 9        | 0.5                        | 0.002                    | 19.99 (20, 20, 20, 20, 20 )                          |

For Arms E and F, respectively, we take the expected ORR to be virtually 0% if epigenetic therapy does not increase the clinical effectiveness of nivolumab alone. We would consider the addition of epigenetic therapy encouraging if the ORR is at least 10%. The study will stop for futility if we see 0 responses among the first 15 patients. We will not consider an

Arm promising if none of the 20 patients on that Arm responds. The following table provides the operating characteristics for Arms E and F, respectively, based on 5000 simulations.

#### Simulation Results for Arm E and for Arm F

| Scenario | Assumed true response rate | Pr(Stop for inferiority) | Average # patients treated (10%, 25%, 50%, 75%, 90%) |
|----------|----------------------------|--------------------------|--|
| 1        | 0.025                      | 0.683                    | 16.58 (15, 15, 15, 20, 20 )                          |
| 2        | 0.05                       | 0.462                    | 17.69 (15, 15, 20, 20, 20 )                          |
| 3        | 0.1                        | 0.206                    | 18.97 (15, 20, 20, 20, 20 )                          |
| 4        | 0.15                       | 0.085                    | 19.58 (20, 20, 20, 20, 20 )                          |
| 5        | 0.2                        | 0.037                    | 19.82 (20, 20, 20, 20, 20 )                          |
| 6        | 0.25                       | 0.013                    | 19.93 (20, 20, 20, 20, 20 )                          |
| 7        | 0.3                        | 0.006                    | 19.97 (20, 20, 20, 20, 20 )                          |
| 8        | 0.35                       | 0.002                    | 19.99 (20, 20, 20, 20, 20 )                          |
| 9        | 0.4                        | 0                        | 20 (20, 20, 20, 20, 20 )                             |

#### 10.5 Feasibility monitoring

We will use separate Bayesian calculations to monitor the feasibility of each treatment. We define feasibility as the ability for a patient to take their full course of their assigned treatment (minimum of six cycles) through 24 weeks, except for progression or death. If there is considerable probability ( $\geq 67\%$ ) that the regimen is feasible for less than half of the patients, we will consider stopping the study. We will base the decision on the posterior probability that the treatment is not feasible ( $> 50\%$  of patients who do not progress or die before 24 weeks do not make it to 24 weeks). The prior distribution for this calculation is Uniform (0,1). We will apply the monitoring rule separately by treatment group, and the analysis will occur at the time of each interim analysis. For each treatment Arm, though, we will apply the rules to all patients pooled together, rather than separately within each subtype, since we do not expect one group to be at greater risk of toxicity than the other. We will consider stopping the study if the data indicate that the treatment regimen is feasible for less than half of all patients, where we quantify certainty as two thirds or greater (i.e., 2:1 odds it is not feasible).

Rule: Stop if there is two-thirds (2:1 odds) or greater probability that 50% or more patients cannot complete at least 6 cycles of therapy (24 weeks), unless the patient's disease progressed or the patient died. The following table shows the stopping boundaries for monitoring that starts at the fifth patient.

| Stop if not feasible for | Probability that feasibility > 50% = |
|--------------------------|--------------------------------------|
| 4 out of 5 patients.     | 0.891                                |
| 4 out of 6 patients.     | 0.773                                |
| 5 out of 7 patients.     | 0.855                                |
| 5 out of 8 patients.     | 0.746                                |
| 6 out of 9 patients.     | 0.828                                |
| 6 out of 10 patients.    | 0.726                                |
| 7 out of 11 patients.    | 0.806                                |
| 7 out of 12 patients.    | 0.709                                |
| 8 out of 13 patients.    | 0.788                                |
| 8 out of 14 patients.    | 0.696                                |
| 9 out of 15 patients.    | 0.773                                |
| 9 out of 16 patients.    | 0.685                                |
| 10 out of 17 patients.   | 0.760                                |
| 10 out of 18 patients.   | 0.676                                |
| 11 out of 19 patients.   | 0.748                                |
| 11 out of 20 patients.   | 0.668                                |

The table below shows the operating characteristics of this monitoring rule for the study. The results are based on 5000 simulated studies for each scenario.

| Assumed true risk
not feasible | Percent of times the study
stops for lack of feasibility | Average sample size |
|-----------------------------------|---|---------------------|
| 0.05                              | 0.1%  | 20.0                |
| 0.10                              | 0.8%  | 19.9                |
| 0.15                              | 2.6%  | 19.6                |
| 0.20                              | 6.3%  | 19.1                |
| 0.25                              | 12.2%   | 18.2                |
| 0.30                              | 18.0%   | 17.4                |
| 0.35                              | 28.8%   | 16.0                |
| 0.40                              | 40.7%   | 14.6                |
| 0.45                              | 54.1%   | 12.9                |
| 0.50                              | 67.5%   | 11.2                |
| 0.55                              | 79.5%   | 9.6                 |
| 0.60                              | 88.3%   | 8.3                 |
| 0.65                              | 94.3%   | 7.1                 |
| 0.70                              | 98.2%   | 6.2                 |
| 0.75                              | 99.6%   | 5.7                 |

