#### **4.4 Duration of Therapy**

Arm D: Epigenetic therapy (azacitidine and entinostat) in combination with nivolumab will be given for six 28-day cycles on this protocol. Patients experiencing adverse event(s) that in the view of the treating physician or principal investigator make six cycles undesirable, may continue with Nivolumab as a single agent after only 2 cycles of concurrent epigenetic therapy with Nivolumab. Please see section 4.4.1 regarding treatment at time of progressive disease (PD).

Arm E and Arm F: Epigenetic therapy (azacitidine and entinostat) in combination with nivolumab will be given for six 28-day cycles on this protocol. Patients experiencing adverse event(s) that in the view of the treating physician or principal investigator make six cycles undesirable, may continue with Nivolumab as a single agent after only 2 cycles of concurrent epigenetic therapy with Nivolumab. Please see section 4.4.1 regarding treatment at time of progressive disease (PD).

Nivolumab monotherapy on all Arms may continue until one of the following criteria applies and at that time, nivolumab treatment will be permanently discontinued:

- Any Grade  $\geq 2$  drug-related uveitis, eye pain or blurred vision that does not respond to topical therapy and does not improve to Grade 1 severity within the re-treatment period OR requires systemic treatment
- Any Grade 3 non-skin, drug-related adverse event lasting  $> 7$  days, with the following exceptions for laboratory abnormalities, drug-related bronchospasm, hypersensitivity reactions, and infusion reaction:
  - Grade 3 drug-related bronchospasm, hypersensitivity reaction, or infusion reaction of any duration requires discontinuation
  - Grade 3 drug-related laboratory abnormalities do not require treatment discontinuation except:
    - Grade 3 drug-related thrombocytopenia  $> 7$  days or associated with bleeding requires discontinuation
    - Any drug-related liver function test (LFT) abnormality that meets the following

criteria require discontinuation:

- AST or ALT > 5-10x ULN for > 2 weeks
- AST or ALT > 10x ULN
- Total bilirubin > 5x ULN
- Concurrent AST or ALT > 3x ULN and total bilirubin > 2x ULN

- Any Grade 4 drug-related adverse event or laboratory abnormality, except for the following events which do not require discontinuation:
  - Grade 4 neutropenia  $\leq$  7 days
  - Grade 4 lymphopenia or leucopenia

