### Feasibility

Feasibility for the purposes of this study means the ability for a patient to take the full course of their assigned treatment (minimum of six cycles) through 24 weeks, except for progression or death.

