### 10.4 Interim Analyses

The study design calls for interim futility analysis by arm. These analyses will occur separately by arm once 10 patients are on an arm and have either received at least 6 cycles of therapy or experienced a PFS event. Subsequent analyses will occur after 15 patients have either received at least 6 cycles of therapy or experienced a PFS event. The final analysis will occur after 20 patients have entered and received full therapy (6 cycles). The futility analysis is based on Bayesian hypothesis testing.

For Arm D, we take the expected ORR to be 20% if epigenetic therapy does not increase the clinical effectiveness of nivolumab alone. This estimate is based on results of the Checkmate studies (CheckMate 057 (non-squamous NSCLC) ORR = 19%; CheckMate017 (squamous cell NSCLC) ORR = 20%). We would consider the addition of epigenetic therapy encouraging if the ORR is 35% or higher. The study will stop for futility if we see 0 responses among the first 10 patients or no more than 1 response in the first 15 patients. We will not consider this Arm promising if we see 3 or fewer responders out of 20 patients. The following table provides the operating characteristics for Arm D based on 5000 simulations.

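### The feasibility rule excepts death whatever its cause, so a treatment-related death on therapy never counts as infeasible, and its wordings can differ on a toxicity stop followed by progression

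*Combined protocol and SAP*

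**What the plan says.** - **Definition.** Section 10.1.2 (Feasibility) defines it as the ability to take the full assigned course, at least six cycles, "through 24 weeks, except for progression or death". Section 10.5 repeats this.
- **Decision quantity.** Section 10.5 bases the decision on the posterior probability that more than 50% "of patients who do not progress or die before 24 weeks do not make it to 24 weeks". The prior is Uniform(0,1) and the threshold is two thirds.
- **Rule sentence.** Stop if that probability is reached for half or more being unable to complete six cycles, unless the patient's "disease progressed or the patient died".
- **Purpose.** Section 10.5 justifies pooling within an arm by saying that toxicity risk is not expected to differ between groups.
- **Timing.** Section 10.5 says "the analysis will occur at the time of each interim analysis". Section 10.4 sets those looks once 10, then 15, patients on an arm "have either received at least 6 cycles of therapy or experienced a PFS event".
- **Tables.** Boundaries are printed for 5 to 20 patients, followed by simulated stopping rates: "The table below shows the operating characteristics of this monitoring rule for the study".
- **Early change of treatment.** Section 4.4 says patients with adverse events "may continue with Nivolumab as a single agent after only 2 cycles of concurrent epigenetic therapy with Nivolumab".

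**The concern.** No wording limits the death exception by cause. A patient killed by the regimen during cycle 3 is treated like one who dies of lung cancer: neither counts as a feasibility failure. For a rule linked to toxicity, the most severe toxicity outcome is the one that cannot count.

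The second problem is order of events. A patient stops for toxicity at week 8 and progresses at week 16. The definition ties the exception to the inability to complete, so it can be read to count this patient, because toxicity ended the course. The decision quantity restricts attention to patients with neither progression nor death before week 24, so it drops the same patient. The rule sentence has no time window and no link to the reason for stopping, and can be read either way.

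Futility in 10.4 uses response only, so this is the one stated arm-level tolerability boundary in Section 10. Two analysts with the same data could report different answers to the monitoring committee.

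**Working it through.** **1. The plan's boundaries.** With a Uniform(0,1) prior and k infeasible out of n, the posterior is Beta(1+k, 1+n−k). Then P(infeasible risk > 0.5) = P(Bin(n+1, 0.5) ≤ k).

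- 4 of 5: 57/64 = 0.891
- 6 of 10: 1486/2048 = 0.726
- 11 of 20: 0.668

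All 16 printed rows reproduce, and each k is the smallest that reaches 2/3.

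**2. One patient.** Assumed counts among 10 patients: 2 progress first, 4 stop for toxicity and are alive and progression-free at week 24, 3 complete, and there is one further patient. That patient either dies of treatment on therapy, or stops for toxicity and then progresses.

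- Decision wording: the patient is dropped, leaving 4 of 7. P(Bin(8, 0.5) ≤ 4) = 163/256 = 0.637, below 2/3: continue.
- Classified by first event: the patient counts, giving 5 of 8. P(Bin(9, 0.5) ≤ 5) = 382/512 = 0.746, a printed stop boundary.

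**3. Sensitivity to assumed rates.** The documents give no fatal or toxicity-stop rate for the concurrent regimen. Section 6.3 reports nivolumab pneumonitis in about 3%, with 3 fatalities, but no denominator for the deaths. Assume progression first 0.40, toxicity stop t = 0.20, a fraction f = 0.5 of these later progressing or dying before week 24, and non-progression death d. The remainder complete.

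Infeasible share among evaluable patients at d = 0.03:

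- Decision wording: t(1−f)/(1−0.40−d−tf) = 0.10/0.47 = 0.213
- By reason, deaths excepted: t/(1−0.40−d) = 0.20/0.57 = 0.351
- First event, all such deaths counted: (t+d)/(1−0.40) = 0.23/0.60 = 0.383

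Exact probability of stopping with looks after 10 and 15 treated patients (stop if at least 5 are evaluable and the posterior is at least 2/3):

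| d | Decision wording | By reason, deaths excepted | First event, all deaths counted |
|---|---|---|---|
| 1% | 1.2% | 9.3% | 10.6% |
| 3% | 1.4% | 10.4% | 14.8% |
| 5% | 1.6% | 11.7% | 19.8% |

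The death exception alone (last column minus the third) is worth about 1, 4 and 8 points. These are upper limits for treatment-related death, because d includes every non-progression death. The gap between the first two result columns depends on f. At d = 3% the decision wording gives 10.4%, 4.8%, 1.4% and 0.1% for f = 0, 0.25, 0.5 and 0.75, against 10.4% by reason throughout.

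**4. Operating characteristics (a separate point).** Exact binomial recursion at 50% infeasibility:

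- Printed in 10.5: 67.5%
- Printed boundaries, every patient from 5 to 20: 61.6%
- Looks at 10 and 15 evaluable patients only: 43.0%
- As the second line, but stopping at 3 of 5 on the first look: 67.7%

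The printed table therefore matches a first look at 3 of 5. That posterior is 42/64 = 0.656, below the stated 2/3.

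**The case against.** The strongest reply is that feasibility is defined here as a completion measure. Deaths are reportable serious adverse events (6.5), and the Safety Monitoring Committee oversees the trial (6.6.4). Section 10.5 mostly speaks of considering a stop. This stands in part: a treatment-related death would be seen. However, none of these provisions sets an arm-level threshold, and the rule sentence itself is worded as an instruction to stop.

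It can also be said that 10.5 names its decision quantity and that the other wordings can be read to agree with it. That is possible, so the definition does not flatly contradict the decision wording. But the text does not settle which reading applies, and under the decision wording a toxicity failure is erased by a later event.

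Two stronger readings are tempting and not supported. A reader might infer from "feasible for less than half of all patients" that excepted deaths stay in the denominator as non-events, giving 4 of 10 and 0.274 in the example. That phrase follows the sentence on pooling patients within an arm and most naturally continues it. A reader might also infer from the 10.4 trigger that a patient who stops for toxicity, alive and progression-free, is left out of the count. Section 10.4 sets when a look happens, not who is counted.

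**Conclusion.** The point holds and should be fixed. That a treatment-related death ending therapy never counts as infeasible follows from every wording and needs no assumption. That a toxicity stop followed by progression can be counted or dropped follows from comparing the definition with the decision quantity.

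The certain size is modest: one patient can move an arm across a boundary, as in 0.637 against 0.746. A reader might take the table above as the expected loss of protection. It is not, because its rates are assumed, and with a 10% toxicity stop rate the decision wording and the reading by reason differ by less than one point (about 0.1% against 0.6% to 0.8% for d of 1% to 5%). Nor do the documents support saying that fatal toxicity goes unmonitored; the gap is in the numeric rule.

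The mismatch in the operating characteristics is a separate error and does not arise from the handling of deaths.

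**What to change.** Use one wording in 10.1.2 and in the definition, decision quantity and rule sentence of 10.5. Classify each patient by the first event that ended the assigned course before week 24.

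- **Excepted:** the first event is progression, or a death not attributed to study treatment.
- **Not feasible:** a death at least possibly related to study treatment on the 6.4 attribution scale; a toxicity stop, regardless of later progression or death; and the other non-completions the definition already counts.

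State whether the early move to nivolumab alone in 4.4 counts as non-completion, and whether initial or confirmed progression (4.4.1) is the excepted event.

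At each look, count a fixed cohort: the first 10, then the first 15 patients on the arm. Classify them after 24 weeks of potential follow-up, or once every member is resolved, with a toxicity stop counting as resolved. Do not count everyone whose status happens to be known. Failures become known before completions, which would bias the rule towards stopping.

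Keep the printed boundaries, with n labelled as feasibility-evaluable patients. Separately, restate the operating characteristics for the stated looks and boundaries.

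**Cost.** Rewording, one rerun of the simulation, and recording the primary reason for stopping and the attribution of each death; the expedited SAE reports in 6.5.1 already ask for a causal assessment where available. The chance of pausing an arm rises slightly. In an assumed tolerable scenario (progression 40%, toxicity stop 10%, half later progressing or dying), it goes from about 0.1% under the decision wording to at most 0.8%, 1.6% and 2.9% at 1%, 3% and 5% non-progression death. Those ceilings are reached only if every such death is treatment-related.

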## 2.4 Rationale for combining epigenetic therapy with immunotherapy

### 2.4.1 Clinical Rationale for combination epigenetic and immunotherapies

Due to 2015 FDA-approval of nivolumab in the 2nd line treatment setting of advanced or metastatic NSCLC, this protocol was previously amended to update nivolumab administration to be given concurrently starting at the initiation of combination study treatment. Therefore, for those patients randomized to combination therapy, nivolumab will be given in combination with epigenetic therapy for 6 cycles, followed by nivolumab monotherapy until disease progression. This will provide patients treated with maximal exposure to both epigenetic therapy and the immune checkpoint inhibitor, in keeping with standard of care practice. In this manner, patients will have longer exposure to the

potential benefits of both epigenetic therapy and immune checkpoint inhibition. This update in therapy is further supported by data indicating that 58.3% (14/24) patients were unable to receive two months of epigenetic therapy alone ("priming") prior to initiation of nivolumab in an earlier therapeutic intervention in this trial (Arm A), due to both symptoms (nausea, vomiting, fatigue, pain) and subsequent rapid disease progression on epigenetic therapy alone.

[figure not shown]
Importantly, the concurrent administration of epigenetic therapy and immune checkpoint inhibition is hypothesized to quickly combine the immune attraction signals from epigenetic therapy with the initial immune-tolerance inhibiting activity of immune checkpoint blockade, and allow the patient's tumor to be exposed to this interaction for a longer and perhaps more significant length of time than in the previous treatment arm. This is supported by pre-clinical data for the combination of these agents' mechanisms of action on efficacy and overall tolerability as detailed below.

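### The 10.5 feasibility count can be read to drop patients who stopped epigenetic therapy for toxicity and later progressed, and its operating-characteristics table assumes looks that the plan does not schedule

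*Combined protocol and SAP*

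**What the plan says.** Section 10.1.2 defines feasibility as the ability to "take the full course of their assigned treatment (minimum of six cycles) through 24 weeks, except for progression or death". Section 10.5 repeats the definition and then sets the decision quantity: the posterior probability, under a Uniform(0,1) prior, that more than 50% of "patients who do not progress or die before 24 weeks do not make it to 24 weeks". The Rule line stops at a probability of two thirds or more and exempts a patient "unless the patient's disease progressed or the patient died". The same section also speaks of feasibility for less than half of all patients.

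Section 4.4 allows patients on Arms D, E and F with adverse events to step down: they "may continue with Nivolumab as a single agent after only 2 cycles of concurrent epigenetic therapy with Nivolumab".

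On timing, 10.5 says "the analysis will occur at the time of each interim analysis". Under 10.4 the first interim comes "once 10 patients are on an arm and have either received at least 6 cycles of therapy or experienced a PFS event", and the next at 15 patients. Yet the printed boundaries are described as monitoring from the fifth patient and run to 20. The operating-characteristics table reports average sample sizes from 20.0 down to 5.7.

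**The concern.** A patient who gives up the epigenetic drugs for toxicity in cycle 3, continues nivolumab and progresses at week 20 could not take the regimen. The literal decision quantity leaves this patient out, because it conditions on being alive and progression-free to week 24. It does not ask which event came first. If such patients leave the count, a look can report no feasibility problem when most of the arm could not tolerate the combination. This is the only numerical rule in Section 10 for halting an arm on tolerability; the futility rules count responses.

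The table is a second problem. It tells the team how often an infeasible arm would be caught, but for a monitoring schedule different from the one in the text.

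**Working it through.** **Inputs.** From 10.5: Uniform prior, threshold 2/3, printed boundaries. From 10.4: looks at 10 and 15. Progression rates by week 24 are assumed; the documents give none.

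**Printed boundaries.** With x failures among n counted, the posterior is Beta(1+x, 1+n−x), so P(rate > 0.5) = P(Bin(n+1, 0.5) ≤ x).
- 4/5: 57/64 = 0.891
- 6/10: 1486/2048 = 0.726

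All 16 printed values reproduce.

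**Two readings, same 10 patients (6 toxicity stops, 4 completers).**
- Every toxicity stop counted: 6/10 = 0.726, stop.
- One of the 6 later progresses and is dropped: 5/9, 638/1024 = 0.623, continue.
- Three of the 6 dropped: 3/7, 93/256 = 0.363, continue.

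With 7 toxicity stops it takes three later progressions to lose the flag (4/7 = 0.637). With 8 it takes five (3/5 = 0.656).

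**Size of the loss.** Suppose 60% of an arm stops for toxicity.
- Progression 40% whether or not the patient switched: counted rate = 0.6×0.6 / (0.6×0.6 + 0.4×0.6) = 0.60. The rate is unchanged; only the number counted falls, to 6 of 10 on average.
- Progression 70% after a switch, 40% otherwise: counted rate = 0.6×0.3 / (0.6×0.3 + 0.4×0.6) = 0.18/0.42 = 0.43.

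With looks at 10 and 15 and at least 5 countable patients, literal-reading stopping is 58.5% in the first case and 15.5% in the second. Without the 5-patient minimum it is 61.1% and 27.7%. In the unrelated case at 40/50/60% progression it is 58.5/51.0/38.5% with the minimum and 61.1/59.0/57.9% without. So much of that decline comes from the minimum count. The chance of fewer than 5 countable at the first look, where no boundary is printed, is 17/38/63%.

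**Operating-characteristics table.** An exact calculation with a look after every patient from 5 to 20, all counted, matches all 15 rows within 1 percentage point, but only with a boundary of 3/5 at the fifth patient. That posterior is 0.656, below 2/3. With the printed 4/5, risk 0.60 gives 86.4% and an average of 9.4.

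With looks at 10 (boundary 6) and 15 (boundary 9) and no exclusions, at risk 0.60:
- P(stop at 10) = 0.633; P(stop first at 15) = 0.076; total 0.709.
- Average n = 10×0.633 + 15×0.076 + 20×0.291 = 13.3.

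The table prints 88.3% and 8.3. With a first look at 10, no average can be below 10, yet the five rows from risk 0.55 to 0.75 print 9.6 down to 5.7.

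**The case against.** The exception for progression or death in 10.1.2 most naturally describes why a patient failed to complete, and the Rule line can be read the same way. On that reading a toxicity stop stays a failure whatever follows. This stands: a reader might infer that the plan definitely removes these patients, but only the decision sentence forces it. The point is an ambiguity with consequences, not a settled exclusion.

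A reader might also take Arm A as proof that toxicity followed by progression is the expected course. Section 2.4.1 says 14/24 could not receive two months of epigenetic therapy "due to both symptoms (nausea, vomiting, fatigue, pain) and subsequent rapid disease progression on epigenetic therapy alone". It does not attribute the symptoms to drug, the drugs were given without nivolumab, and 2.4.2 blames the aggressiveness of the disease. Arm A does not establish the pattern.

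Excluding patients whose disease progressed first is itself defensible, because it separates intolerance from disease failure. Keeping them in the denominator as non-failures would be worse. If 5 of 10 progress first and 4 of the other 5 stop for toxicity, the present text gives 4/5 = 0.891 (stop), and the diluted count gives 4/10 = 0.274 (continue). With independent competing times and 60% toxicity stops, the diluted count stops about 40/31/23% of the time at 40/50/60% progression, against 59/51/38% under the literal text.

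Finally, the rule says only that stopping will be considered. Toxicities are tabulated for everyone treated (10.6) and the Safety Monitoring Committee oversees the trial (6.6.4), so the events stay visible. That limits the harm but does not settle who is counted.

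On the table, the fifth-patient wording in 10.5 suggests that continuous monitoring may have been intended. If so, the sentence on timing is the one to correct.

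**Conclusion.** The counting point holds as an ambiguity: the literal decision sentence and the milder reading can give opposite answers at the same look, and nothing elsewhere resolves it. No single figure for lost detection can be defended. If switching and progression are unrelated, the loss is mainly in numbers counted. If switched patients progress more often, it is larger; the fall to 15.5% rests on an assumed 70% versus 40% split.

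The table point needs no such assumption. The table does not describe looks at 10 and 15, and at risk 0.60 it overstates stopping by about 17 percentage points (88.3% against 71%) even before any patient is excluded.

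**What to change.** **1. Classify by first event (10.1.2 and 10.5).** A permanent stop of the combination before cycle 6 is complete, for a reason other than progression or death, counts as not feasible even if progression or death follows before week 24. This includes a switch to nivolumab alone under 4.4. Leave out only patients whose progression or death came before any such stop. Doses omitted or reduced under 5.1 with treatment resumed are not failures. Do not add progress-first patients to the denominator as non-failures. Apply the printed boundary for the number actually counted, and say what happens when fewer than 5 are countable.

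Restoring a dropped toxicity stop adds one to both x and n, so it can only raise the posterior. The cost is more stopping of tolerable arms. Assume 30% toxicity stops, 40% progression and independent exponential times. The toxicity-first share is 0.357/(0.357+0.511) × (1−0.7×0.6) = 0.238, where 0.357 = −ln 0.7 and 0.511 = −ln 0.6. Completers are 0.7×0.6 = 0.42, so the counted rate is 0.238/0.658 = 36% rather than 30%. Stopping at the 10 and 15 looks rises from about 6% to about 12%.

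**2. Re-run the operating-characteristics table** for looks at 10 and 15, the printed boundaries and the countable denominator over a stated range of progression rates. Alternatively, state that monitoring is continuous from patient 5, and re-run with the printed 4/5 boundary.

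Both are wording changes plus one short simulation. They need the stop date, stop reason and progression date, and no extra patients, visits or scans.
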